**CCI**

#### **3.2 Study Design**

This is a multicenter, randomized, open label exploratory study, conducted in the US and Canada, evaluating the efficacy and safety of enzalutamide for extension of time to prostate cancer progression (pathological or therapeutic) in subjects with clinically localized, histologically proven prostate cancer that is categorized as low risk or intermediate risk and who are under AS. A total of 222 subjects from approximately 50 centers will be enrolled. Subjects are eligible if they were diagnosed within 6 months of screening and have been on AS. A minimum of ten cores from transrectal ultrasound-guided prostate biopsy (mpMRI targeted versus non-mpMRI targeted) are required; confirmatory biopsy before entering the study is not required and is done at the discretion of the investigator.

Low risk is defined as T1c-T2a, PSA $<$ 10, N0, M0 (or presumed N0, M0 if computerized tomography [CT]/bone scan not done due to low risk of metastases), GS  $\leq$  6, ECOG status  $\leq$  2 and estimated life expectancy  $>$  5 years. Intermediate risk is defined as T2b-T2c, PSA $<$ 20, N0, M0 (or presumed N0, M0 if CT/bone scan not done), GS  $\leq$  7 (3+4 pattern only), ECOG status  $\leq$  2 and estimated life expectancy  $>$  5 years.

Prostate cancer progression is defined as either therapeutic progression or pathological progression. Therapeutic progression is defined as the earliest occurrence of primary therapy for prostate cancer (prostatectomy / radiation / focal therapy / systemic therapy). Pathological progression is defined as increase in primary or secondary Gleason pattern by  $>$  1 or higher

proportion of cancer positive cores (>15% increase). Subjects will be stratified by low versus intermediate risk and type of biopsy performed (mpMRI targeted versus non-mpMRI targeted).

Subjects will be randomized (1:1) either to receive treatment with enzalutamide (160 mg), administered as four 40 mg capsules, by mouth, once daily or to AS during the one year study treatment period. Following the one year treatment period, all subjects will be followed for one additional year. Subjects will be followed up every 3 months for these 2 years, after which follow-up will either be every 6 months or unscheduled until the last subject finished their 2 year follow-up. Serum PSA will be measured at baseline and every 3 months during subsequent follow-up visits.

Digital rectal examination will be done at baseline and every 6 months during subsequent follow-up visits. All subjects will have transrectal ultrasound-guided prostate biopsy (with or without mpMRI targeting) at 12 months and 24 months with a standard of 12 cores required; two biopsies are required from each target site (if mpMRI is used) as well as 12 systematic biopsies (12 core transrectal ultrasonography [TRUS] guided systematic biopsies including six lateral and six mid lobar cores from the base, middle and apex of the gland) at the same time. All sites will be consistent with their method of biopsy (with regards to the use of mpMRI targeting) throughout the study for all subjects enrolled at that site. If there is a significant clinical reason such as adverse changes on digital rectal examination or increase in PSA, biopsy is allowed based on investigator's decision. If at any time during the study the subject considers intervention for prostate cancer, biopsy is allowed and recommended.

Treatment decisions based on pathological progression are at the discretion of the individual investigator. Hormonal levels (testosterone, DHT, dihydroepiandrosterone, androstenedione and estradiol) will be collected at baseline, 12 months and 24 months. Quality of life/sexual function questionnaires (EPIC), anxiety measures (MAX-PC), BFI, SF-12 assessments will also be done at baseline, 6 months, 12 months, 18 months and 24 months. An additional BFI assessment will be done at 3 months. Subjects who withdraw from the study before the 24 Month visit will be asked to complete the EPIC, MAX-PC, BFI and SF-12 assessments at their final study visit.

Subjects will be followed beyond the two year study period until the last subject has completed the 24 month visit. This additional follow up will entail biannual visits (every 6 months and/or unscheduled visits) that include measurement of serum PSA and digital rectal exam.

All biopsy samples, including those collected for-cause or per standard of care, will be centrally read by a designated pathologist blinded to treatment allocation. CT, magnetic resonance imaging (MRI) and bone scan will be performed at the discretion of the investigator based on clinical need; when performed, these assessments will be read locally and recorded in the electronic case report form (eCRF).

Throughout the study, safety and tolerability will be assessed by the recording of AEs, monitoring of vital signs, physical examinations and safety laboratory evaluations.

A dose of 160 mg enzalutamide (four 40 mg capsules) once daily, administered orally, is the FDA approved daily dose for the indications in the approved labeling.

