## 6.4 Other Variables

To clearly state, the following variables are defined:

- Month = 30.4375 days. Year = 365.25 days.
- $BMI(kg/m^2) = Weight(kg) / Height(m^2)$
- Age at randomization=  $\text{floor}((\text{intck}(\text{'month'}, \text{birth date}, \text{randomization date}) - (\text{day}(\text{randomization date}) < \text{day}(\text{birth date}))) / 12)$
- Time since initial/histological diagnosis (years) =  $[(\text{date informed consent signed} - \text{date of initial/histological diagnosis}) + 1] / 365.25$ .
- Time since initial diagnosis to Randomization (years) =  $[(\text{date of Randomization} - \text{date of initial diagnosis}) + 1] / 365.25$ .
- The duration of treatment was calculated as the (last dose date – first dose date) + 1.
- Number of pills taken from one visit to the next = number of pills dispensed – number of pills returned.
- Study drug compliance at each visit is calculated as =  $[(\text{number of pills dispensed} - \text{number of pills returned}) / (4 * \text{number of days in the visit period})] * 100$ .
- Baseline results are defined as the last assessment prior to first dose of study drug, for subjects randomized to once daily enzalutamide. For subjects randomized to active surveillance, baseline is defined as the last assessment prior to or on the date of randomization.
- Treatment Emergent Adverse Events (TEAEs) are any AEs occurring on or after date of first study drug dose date (or randomization for AS) until 30 days post-treatment end date (or 1-year plus 30 days for AS).
- Treatment Phase is defined as date of first study drug dose (or randomization for AS) until either 30 days post treatment end date or (if earlier) study discontinuation date.
- 1-Year Follow-Up Phase is defined as 31 days post treatment end date until either completing 1-Year Follow-Up or (if earlier) study discontinuation date.
- Continued Follow-Up Phase is defined as the day after completing 1-Year Follow-Up phase until study discontinuation date.

Study Day is defined using the following step-wise function:

- If date of interest is on or following randomization, Study Day = Date of Interest – Randomization Date + 1;
- Else, Study Day = Date of Interest – Randomization Date.

Change from baseline is the difference between the result on a post baseline visit and baseline assessment.

Rise in serum PSA is defined as  $PSA \geq 25\% \text{ of baseline or } \geq 25\% \text{ above nadir or } \text{absolute increase} > 2\text{ng/mL}$ .

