Progression-free survival is defined as the time (in months) from the date of randomization until the date of the cancer progression (pathological or therapeutic). Pathological progression is defined as increase in primary or secondary Gleason pattern by  $\geq 1$  or higher proportion of cancer positive cores ( $\geq 15\%$  increase). Therapeutic progression is defined as the earliest occurrence of primary therapy for prostate cancer (prostatectomy/radiation/focal therapy/systemic therapy).

Subjects with no cancer progression at the time of trial completion (the last study-wide subject completes a 24 month follow-up visit), discontinuation or death will be censored at the last assessment date. Subjects discontinuing therapy will not be censored until the time of study discontinuation. Additionally, subjects switching therapy during the study will be censored at the time of the initial therapy switch.

For subjects on enzalutamide, TEAEs, defined as an adverse event observed after starting administration of the study drug and until 30 days after treatment end date, are categorized as AEs. If the adverse event occurs on Day 1 and the onset check box is marked “Onset after first dose of study drug” or the onset check box is left blank, then the adverse event will be considered treatment emergent. If the adverse event occurs on Day 1 and the onset check box is marked “Onset before first dose of study drug”, then the adverse event will be categorized as medical history. If a subject experiences an event both during the pre-investigational period and during the investigational period, the event will be considered as an AE only if it has worsened in severity (i.e. it is reported with a new start date). All adverse events collected that begin within 30 days following study discontinuation will also be counted.

Percent positive cores are calculated using the number of systemically-sampled prostate regions and any targeted regions with at least one positive core divided by the total number of systematically-sampled regions and targeted regions. This implies that despite the number of samples within a given systematic or targeted region, any positive core will indicate that region as positive.

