### 7.4.1 Analysis of Primary Endpoint(s)

The primary efficacy endpoint is time to prostate cancer progression (pathological or therapeutic), and the hypothesis for analysis is:

$H_0$ : The time to progression for Enzalutamide and Active Surveillance (AS) are the

same  $H_1$ : The time to progression for Enzalutamide and AS are not the same

Median and 95% confidence intervals for time to prostate cancer progression (pathological or therapeutic) will be calculated with the Kaplan-Meier (KM) method for each treatment group. Subjects with no cancer progression at the time of trial completion, discontinuation or death will be censored at the last assessment date. Additionally, subjects switching therapy during the study will be censored at the time of the initial therapy switch, but subjects discontinuing therapy will not be censored until the time of study discontinuation. If less than 50% of subjects progress by study cut-off time, the 25th percentile and its two-sided 95% confidence interval will be reported. KM plots will be generated.

Treatment group differences between enzalutamide versus AS will be based on a Cox regression model. The resulting Hazard ratio (enzalutamide/AS) and 95% confidence interval will be included in the summary. Censoring assumptions will follow the same rules as applied for the KM estimates. Fixed effects for the model will include the treatment groups, randomization stratification factors [prostate cancer risk (low/intermediate), type of biopsy performed (mpMRI targeted/non mpMRI targeted)], age, race, and time since prostate cancer diagnosis. Additionally, a random effect of site will be included in the model.

The association between the survival time, log of time to disease progression, and survival probability, log negative log, will be investigated graphically by Cox proportional-hazards models. If the proportional hazards assumption is violated, appropriate remedial methods will be investigated and applied.

Data listings will be provided.

In addition to an overall analysis, the primary and secondary analyses will be repeated for pathological progression and therapeutic progression, individually.

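### SAP Sections 3.2 and 6.4 define pathological progression with different Gleason thresholds (>1 versus ≥1), so a one-step upgrade is a primary-endpoint event under one section and not under the other

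*SAP*

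**What the plan says.** SAP Section 3.2 (Study Design) defines pathological progression by an "increase in primary or secondary Gleason pattern by $>$ 1 or higher" "proportion of cancer positive cores (>15% increase"). The two quotes are consecutive: the words after the 1 begin the core criterion.

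SAP Section 6.4 (Other Variables) opens with "To clearly state, the following variables are defined" and defines the same term by an "increase in primary or secondary Gleason pattern by $\geq 1$ or higher proportion of cancer positive cores ( $\geq 15\%$ increase").

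Section 6.1.1 makes pathological progression one of the two components of the primary endpoint; therapeutic progression is the other. Section 7.4.1 analyses time to progression without restating the definition and adds that "the primary and secondary analyses will be repeated for pathological progression and therapeutic progression, individually". Section 8, which lists departures from the protocol, does not mention the difference. No text says which section takes precedence.

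On entry, Section 3.2 allows a Gleason score of at most 6 for low risk. For intermediate risk it allows at most 7, with the restriction "3+4 pattern only". Biopsies "will be centrally read by a designated pathologist blinded to treatment allocation".

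**The concern.** Two analysts who each follow one section of the same SAP would derive different primary-endpoint events from the same pathology readings. Entry is restricted to low Gleason scores, so the disputed category is the smallest upgrade from the baseline patterns that the trial admits. Under Section 3.2 the Gleason criterion would need a pattern 5 from a 3+3 baseline, and a primary pattern 5 from a 3+4 baseline.

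A subject with a one-step upgrade may still become an event through the core criterion or through primary therapy, so the composite endpoint is partly protected. The separate analysis of pathological progression is not protected in this way, because a later therapy cannot restore a pathological event that the rule excluded.

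Blinded central reading protects the readings. It does not settle which operator the derivation applies to them. The study is open label, so the event rule should be unambiguous before lock.

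**Working it through.** **1. The two definitions side by side**

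| Criterion | Section 3.2 | Section 6.4 |
|---|---|---|
| Increase in primary or secondary Gleason pattern | >1 (two or more steps) | ≥1 (one or more steps) |
| Increase in share of positive cores | >15% | ≥15% |

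The words 'or higher' after the threshold in Section 3.2 do not turn >1 into 1 or higher. They introduce the core criterion, and Section 6.4 has the same construction.

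**2. Which upgrades are affected**

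Assumption: baseline is 3+3 or 3+4 (entry criteria, no pattern below 3), and follow-up patterns run from 3 to 5. Let d be the larger of the change in primary pattern and the change in secondary pattern.

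| Baseline | d = 1 (event under 6.4 only) | d = 2 (event under both) |
|---|---|---|
| 3+3 | 3+4, 4+3, 4+4 | 3+5, 4+5, 5+3, 5+4, 5+5 |
| 3+4 | 3+5, 4+3, 4+4, 4+5 | 5+3, 5+4, 5+5 |

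That gives 3 + 4 = 7 discordant pairs and 5 + 3 = 8 concordant pairs, 15 in all. The pairs are not equally likely, so 7 of 15 is a count of cases and not an estimate of the share of events.

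**3. The plan's own event figure (Section 4)**

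Inputs: hazards 0.2310 (control) and 0.1189 (treatment), 1:1 allocation, two-sided alpha 0.05, power 80%.

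- Hazard ratio: 0.1189 / 0.2310 = 0.5147, stated as 0.52.
- Schoenfeld: events = 4 × (1.960 + 0.842)² / (ln HR)². With 0.5147 this gives 72, the stated figure. With the rounded 0.52 it gives 74.
- Expected events from 222 subjects, with uniform accrual over 1 year, 3 years in total and exponential loss of 16% over 3 years: 72.1.

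The design figure reproduces and is not in dispute.

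**4. What a loss of events would do**

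The SAP gives no frequency of one-step upgrades, so the net losses below are assumptions. They also take the 72 events as planned under ≥1 and the hazard ratio as the same under both definitions.

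Power = Φ(√d / 2 × |ln HR| − 1.96), where d is now the number of events.

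| Net loss | Events | Power, HR 0.5147 | Power, HR 0.52 |
|---|---|---|---|
| 0% | 72 | 80.4% | 79.2% |
| 10% | 64.8 | 76.2% | 74.9% |
| 25% | 54 | 68.4% | 67.1% |
| 50% | 36 | 51.3% | 50.1% |

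**5. The core operator**

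The two signs differ only at an increase of exactly 15%. Read as percentage points, with 12 regions at both biopsies, 15 points is 0.15 × 12 = 1.8 regions, which cannot occur. With unequal denominators it can. The baseline biopsy needs only 10 cores and follow-up takes 12 plus any targets. If each core is one region, 1/10 to 3/12 is 10% to 25%, exactly 15 points. Likewise 3/12 to 6/15 is 25% to 40%. These cases should be rare.

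**The case against.** The strongest reply is that Section 3.2 is a design narrative while Section 6.4 is the definitional section. Section 6.4 also holds the censoring rules and the derivation of percent positive cores, so a programmer would naturally build the endpoint from it. If so, no event is lost and the defect is one of wording. That is the likely intention, but the SAP does not say so. Section 6.4 is also not fully reliable on operators: its PSA rule uses a strict >2 ng/mL where Sections 3.1 and 6.1.2 use ≥2. This is why the choice needs confirming against the protocol.

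The strict sign in Section 3.2 could be a typographical or file-conversion loss of the bar under ≥. This cannot be excluded. However, ≤ signs are intact in Section 3.2 and ≥ signs in Section 3.1, and both progression thresholds in Section 3.2 are strict.

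It is also fair to say that the power scenarios do not measure the defect. Section 4 takes its assumptions from an outside study and ties them to neither definition, and nothing in the SAP bounds the share of one-step upgrades. The scenarios show only what is at stake over a range.

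None of this removes the contradiction in the text.

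**Conclusion.** The concern holds. As written, the SAP gives two incompatible Gleason rules for a component of the primary endpoint and does not rank them. Following Section 3.2 would drop every upgrade of exactly one step from the Gleason criterion. From a 3+3 or 3+4 baseline that is 7 of the 15 possible upgrading pairs, assuming no baseline pattern below 3 and follow-up patterns of 3 to 5.

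The number of events affected cannot be derived from the SAP. Over the assumed range of 10% to 50% net loss, power would fall from about 80% to between about 76% and 51%. If the derivation already follows Section 6.4, the numerical effect is nil, but the text still needs correcting. The core operator is a minor part of the same inconsistency. Because this is the event rule of the primary endpoint, it must be fixed before database hard lock.

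**What to change.** Before database hard lock, put one definition of pathological progression in both places. Change Section 3.2 to the operators of Section 6.4 (Gleason increase ≥1, core increase ≥15%), after confirming them against the protocol. If the protocol differs, resolve that explicitly and record it in Section 8.

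In the same sentence, state whether the 15% is in percentage points of the percent-positive variable of Section 6.4 or relative to baseline, since neither section says.

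Then check the derivation program against the agreed wording.

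The cost is one line of SAP text and a program check. No new data, biopsy readings or visits are needed.

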### **3.3 Randomization**

Randomization will be performed on Study Day 1 via Interactive Response Technology (IRT). Prior to the initiation of the study treatment, the site staff will contact the IRT in order to determine the randomly assigned treatment. Specific procedures for randomization through the IRT are contained in the study procedures manual.

The randomization allocation will consist of 1:1 ratio for once daily enzalutamide or AS. The randomization will be stratified according to the following two factors:

- Low versus intermediate risk
- Type of biopsy performed (mpMRI targeted versus non-mpMRI targeted)

Additionally, enrollment of subjects with low risk prostate cancer will be capped to not exceed 80% of the study population.

## 4 SAMPLE SIZE

This study is designed to evaluate time to prostate cancer progression (pathological or therapeutic progression) as the primary endpoint. The overall two-sided type I error for this study is set at 0.05 level. The characteristics of time to prostate cancer progression (pathological or therapeutic progression) are used to determine the total sample size and overall duration.

A sample size of 222 subjects randomized in a 1 to 1 manner accrued over one year, a study duration of 3 years, loss-to follow-up of 16%, an assumed underlying hazard ratio of 0.52 and a three year median time-to-progression for the Control group (0.2310 rate) will result in 72 events (Fleshner et al., 2012). This sample size is sufficient to power this study at 80% with a two-sided type I error rate of 5%.

The assumed hazard ratio of 0.52 is consistent with Fleshner et al. (2012). Specifically, the Fleshner study is powered to detect a 39% failure rate reduction in the treated group with respect to a three year 45% failure rate in the control group. We used a more conservative 30% failure rate reduction for the treated group and a 50% three year failure rate for the control group. This resulted in parameter estimates of 0.2310 for the Control group and 0.1189 for the Treatment group, and thus, resulted in the hazard rate of 0.52.

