**Table 2 Schedule of Assessments**

Study Visit Name	Screening	Randomization	3m	6m	9m	12m	15m	18m	21m	24m	>24m, q6m 	Unscheduled 
Study Day	-28 to -7	1	85	176	267	358	455	545	635	730	>730	n/a
Week	-4 to -1	1	13	26	39	52	65	78	91	104	>104	n/a
Window (days)			± 7	± 7	± 7	± 7	+7	+7	+7	+7	± 7	n/a
Informed Consent	X											
Medical History 	X		X 									
Inclusion/Exclusion Criteria	X		X									
Randomization		X										
Vital Signs	X		X	X	X	X	X	X	X	X	X	X
Physical Examination, Weight 	X			X	X	X	X	X	X	X	X	X
12-Lead ECG	X 											
MUGA/Echocardiogram 	X 											
Clinical Labs 	X		X	X	X	X	X	X	X	X	X	X
Serum hormone levels 		X			X				X			X
Serum PSA 	X		X	X	X	X	X	X	X	X	X	X 
Digital Rectal Examination	X			X		X		X		X		X 
Transrectal ultrasound-guided prostate biopsy(12 core) 	X 				X				X			X 
BFI 		X	X	X		X		X		X		
SF-12 		X		X	X		X		X		X	
EPIC 		X		X	X		X		X		X	
MAX-PC 		X		X	X		X		X		X	
Adverse Events 	X		X	X	X	X	X	X	X	X	X	X
Concomitant Medications	X		X	X	X	X	X	X	X	X	X	X
Therapies and Outcomes Review	X		X	X	X	X	X	X	X	X	X	X
Study Drug Dispensing 	X		X	X	X	X						
Blood Sample for Potential Future Analysis(optional) 	X		X	X	X	X	X	X	X	X	X	X

1. Subjects will be followed every 6 months until the last subject (study-wide) has completed the 24m Visit.
2. Unscheduled visits may be performed at any time during the study whenever necessary to assess for or follow-up on adverse events (AEs), at the subject's request or if deemed necessary by the investigator.
3. Medical history will include capturing information about any first degree relatives with prostate cancer. Any updates to the subject's medical history will be recorded at the Randomization Visit (Study Day 1) prior to randomization.
4. A complete physical examination will be completed at the Screening Visit. For all visits after the Randomization visit, only a brief physical examination is required.
5. This procedure (if required) must be done within 28 days prior to randomization.
6. A multi-gated acquisition (MUGA) scan or echocardiogram is only required if the subject has a history of anthracycline or anthracenedione (mitoxantrone) treatment.

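### Section 4's 72 events and 80% power assume progression is fully detected to year 3, but scheduled biopsies stop at month 24, so about 11 of the 72 events depend on for-cause biopsy or a therapy start

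*SAP*

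**What the plan says.** SAP Section 4 plans 222 subjects randomized 1:1, "accrued over one year, a study duration of 3 years, loss-to follow-up of 16" per cent, a hazard ratio of 0.52 and yearly rates of 0.2310 (control) and 0.1189 (enzalutamide). It expects 72 events and states: "This sample size is sufficient to power this study at 80% with a two-sided type I error rate of 5" per cent.

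On biopsies, Section 3.2 states: "All subjects will have transrectal ultrasound-guided prostate biopsy (with or without mpMRI targeting) at 12 months and 24 months". After month 24 it states: "This additional follow up will entail biannual visits (every 6 months and/or unscheduled visits) that include measurement of serum PSA and digital rectal exam". A biopsy outside the schedule is allowed for a clinical reason such as a PSA rise or a change on rectal examination, and: "If at any time during the study the subject considers intervention for prostate cancer, biopsy is allowed and recommended". In Table 2 the row "Therapies and Outcomes Review" continues at the visits after month 24.

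The endpoint has two components. Pathological progression is a change in Gleason pattern or in positive cores, so it needs a biopsy. For the other component, Section 6.4 states: "Therapeutic progression is defined as the earliest occurrence of primary therapy for prostate cancer". The same section also states: "Additionally, subjects switching therapy during the study will be censored at the time of the initial therapy switch". Section 7.4.1 repeats that clause, and plans to repeat the analyses for pathological and therapeutic progression separately.

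**The concern.** Section 4 lets every subject contribute events at a constant rate for 2 to 3 years. The design looks for pathological progression on a schedule for only 2 years. Between month 24 and year 3, a progression becomes an event only if something prompts a biopsy or the subject starts primary therapy. Section 4 does not say that its power depends on this. The stated 80% leaves no margin, so any late progression that goes unseen lowers power, and a non-significant result would be read against a figure that assumes none is missed.

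Two rules elsewhere in the SAP add to this. The therapy route is not secure as written, because the first primary therapy is an event while a therapy switch is censored, and nothing says how the two differ. In the pathological-only analysis, censoring at the last assessment lets a PSA and rectal-examination visit after month 24 count as time free of pathological progression, which such a visit cannot show.

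**Working it through.** **Inputs.** From Section 4: 111 per arm, one-year accrual (taken as uniform), 3-year study, rates 0.2310 and 0.1189 per year, stated HR 0.52 (0.1189/0.2310 = 0.5147), two-sided 5% level. From Section 3.2: biopsies at months 12 and 24. Assumed: the 16% loss is cumulative over 3 years, so the loss rate is g = -ln(0.84)/3 = 0.0581 per year. Section 4 gives no period for the loss.

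**Formulas.** For event rate l, the probability of an observed event by follow-up time u is l/(l+g) × [1 - exp(-(l+g)u)]. Power with d events is Phi(sqrt(d/4) × |ln HR| - 1.96), where |ln HR| is 0.6641 at HR 0.5147 and 0.6539 at HR 0.52.

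**Step 1: reproduce Section 4.** Averaging over u uniform on 2 to 3 years gives 45.5 + 26.6 = 72.1 events. At HR 0.5147, sqrt(72.1/4) × 0.6641 = 2.820 and power is Phi(0.860) = 80.5%. At HR 0.52 the product is 2.776 and power is Phi(0.816) = 79.3%. For 80% power, 71.2 events are needed at 0.5147 and 73.4 at 0.52. So 72 suffices at the unrounded HR and falls just short at the stated one. Loss of 16% over 2 years gives 69.8 events and 16% per year gives 63.4, so the 3-year reading is the one that returns 72.

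**Step 2: events by the last scheduled biopsy.** With u fixed at 2 years, 38.9 + 22.2 = 61.2 events (arms rounded separately). The difference is 72.1 - 61.2 = 10.9 events, and 10.9/72.1 = 15%.

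**Step 3: events seen only at the two scheduled biopsies.** This treats all progression as pathological and requires the subject to be still in follow-up at the next biopsy. Events per arm are 111 × the sum over k = 1, 2 of [exp(-l(k-1)) - exp(-lk)] × exp(-gk), which gives 37.8 + 21.6 = 59.4.

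**Step 4: power by how many late events are found.**

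| Detection | Events | Power, HR 0.515 | Power, HR 0.52 |
|---|---|---|---|
| All to year 3 | 72.1 | 80.5% | 79.3% |
| Half of the late events | 66.6 | 77.4% | 76.1% |
| None after month 24 | 61.2 | 73.8% | 72.5% |
| Months 12 and 24 biopsies only | 59.4 | 72.5% | 71.2% |

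A log-rank simulation (1,500 runs, HR 0.52, same loss) gave 77% with full detection, 71% with none after month 24 and 70% with biopsy-visit detection only, so the drop is not a product of the formula.

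**Step 5: accrual.** Follow-up runs until the last subject completes month 24, so slower accrual lengthens it. With full detection and the same rates, 18-month accrual (u from 2 to 3.5 years) gives about 77 events, and 24-month accrual (u from 2 to 4 years) about 81. The 72 is therefore tied to one-year accrual.

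**Step 6: the treatment rate.** Section 4 describes a 30% reduction from a 50% three-year failure rate. Read as relative, that leaves 0.50 × 0.70 = 35% failure, a rate of -ln(0.65)/3 = 0.1436 and an HR of 0.1436/0.2310 = 0.62. The rate used instead gives 1 - exp(-3 × 0.1189) = 30% failure. At a rate of 0.1436 the same design yields 76.7 events and about 55% power.

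**The case against.** The strongest case against is that 71-74% describes something the SAP does not plan. For-cause biopsy is allowed, biopsy is recommended when intervention is considered, therapy review continues after month 24, and primary therapy is itself an event. Some late progressions will therefore be found, and if half are, the loss is only about 3 points. This stands. A reader might infer that the trial really has 71-74% power; the documents do not support that.

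A reader might also take 72 as the most events the trial can yield. It is not, because slower accrual adds events. Nor is constant hazard clearly generous about events before month 24: no confirmatory biopsy is required at entry, so the month-12 biopsy could find a disproportionate share.

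Third, Section 4 cannot be called sound on all its inputs. The 72 follows from the rates, but the treatment rate does not follow from a relative reading of the described reduction. Every power figure here is conditional on 0.1189.

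It can also be said that an unstated detection assumption is not an error, and that the censoring questions are separate from power. The first is fair as to severity: this is a missing qualification. The second is partly fair, but the therapy clause decides whether a late therapy start counts as one of the 72 events, and that contradiction stands on its own.

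**Conclusion.** The point holds as a qualification of Section 4, not as a calculation error in the 72. About 11 of the 72 events (15%) depend on detection outside the biopsy schedule. The loss of power runs from none to about 8 points: about 3 points if half the late events are found, with a lower bound of about 71-74% if none are. These figures rest on the rates 0.2310 and 0.1189, uniform one-year accrual and 16% loss over 3 years. The share of late events that will be found cannot be derived from the document.

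Two parts do not depend on any of those assumptions: the conflict between censoring at a therapy switch and counting first primary therapy as an event, and the use of visits without a biopsy as evidence of freedom from pathological progression in the component analysis.

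**What to change.** 1. **Section 4.** First reconcile the described 30% reduction with the 0.1189 rate. Then name the HR used and state the conditions. If 0.1189 is kept, text such as: *The 72 events assume one-year accrual, 16% loss over 3 years and detection of progression at a constant rate to year 3. Scheduled biopsies end at month 24; about 11 of the 72 events depend on for-cause biopsy or a therapy start. Power is 80.5% (HR 0.515) or 79.3% (HR 0.52) if all are found and 77.4% or 76.1% if half are. If none are, the lower bound is about 71-74%; this is not the expected power.* Confirm the loss period.

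2. **Sections 6.4 and 7.4.1.** Reconcile the therapy-switch clause with the definition of therapeutic progression, so that a qualifying therapy start is not censored in the primary analysis, and say what a switch then covers.

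3. **Pathological-only analysis.** Censor subjects without pathological progression at the last evaluable biopsy.

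For the composite endpoint, tying the censoring date to therapy review would change almost nothing, since that review takes place at essentially every visit. A table of biopsy completion by arm at months 12 and 24 is optional.

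The cost is a few sentences, one changed censoring date in an analysis already planned, and minor programming. Sample size and primary test stay as they are. The downsides are a less favourable power statement, and in the pathological-only analysis shorter follow-up and an assumption that not having a later biopsy is uninformative.
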